Protocol Title: Video Information Provider for HIV-Associated Non-AIDS (VIP-HANA)

NCT03182738

Date: 04/16/18

Protocol: IRB-AAAP5958

Principal Investigator: [name]

Protocol Title: Video Information Provider for HIV-Associated Non-AIDS (VIP-HANA)

STUDY PURPOSE AND RATIONALE

The purpose of this study is to use technology to improve symptom status and ultimately improve patient centered outcomes in PLWHA. The primary purpose of the intervention (VIP- HANA) is to improve symptom status. We hypothesize that VIP-HANA will improve symptom frequency and intensity, our primary outcomes.

SPECIFIC AIMS

HIV has evolved from an acute to a chronic illness largely due to antiretroviral therapy (ART) (Chiasson, Shaw, Humberstone, Hirshfield, & Hartel, 2009). As a result, people living with HIV/AIDS (PLWHA) are living longer and by 2015 half of PLWHA in the US will be over 50 years old. As PLWHA age, they are developing chronic illnesses and co-morbid conditions that are often seen in older HIV negative patients (Parsons et al., 2005). Fifty to sixty percent of deaths in HIV-infected persons occur from HIV-associated non-AIDS (HANA) causes and people suffering from these conditions are more likely to be affected by adverse symptoms (Parsons et al., 2006). HANA conditions (e.g., cardiovascular disease, liver disease, diabetes, and asthma) are becoming more common as PLWHA age.

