To achieve this aim, we will conduct an online survey with 1,000 PLWHA with HANA conditions, recruited from national social networking websites, to learn about their symptom experience and self-care strategies that they use to mitigate their symptoms. Our study team will incorporate the most frequently reported symptoms and appropriate self-care strategies into our VIP system. The VIP-HANA system, which will provide tailored self-care strategies based on HANA conditions and gender.

Specific Aim 1b: Evaluate the VIP-HANA system for violations of usability principles.

Specific Aim 2: Compare the efficacy of VIP-HANA to a control arm for ameliorating symptom frequency and intensity and secondary health outcomes in 100 PLWHA with HANA conditions over 6 months.

Our hypotheses are that use of VIP-HANA as compared to a control arm will:

- a) Decrease symptom frequency and intensity (primary outcome measures) in the treatment arm as compared to the control arm;
- b) Decrease frailty as measured by Fried’s frailty phenotype;
- c) Improve functional and emotional status, quality of life, and morbidity; and
- d) Improve adherence to antiretroviral therapy (ART).

Specific Aim 3: Understand PLWHA’s perceptions of the predisposing, enabling, and reinforcing factors for VIP-HANA use with theoretically-guided focus group sessions.

We will conduct focus groups, using the PRECEDE-PROCEED model with Aim 2 intervention arm participants, to understand their perceptions related to VIP-HANA use.

DESIGN AND METHODS TABLE

Table 1 presents and overview of the design, participants and data analysis plan

Table 1. Overview of Design, Methods, Participants, and Data Analysis			
Analysis			
Aim	Design/Methods	Participants	Data Analysis
1a	Online Survey	PLWHA with HANA conditions(N=1000) and PLWHA without HANA conditions (N=1000)	Descriptive and thematic analysis of most frequently reported symptoms, symptom attribution, self-care strategies and information source.

1b	Heuristic evaluation, Usability testing (including: cognitive walkthrough, user testing using think-aloud protocol)	Heuristic evaluation: human-computer interaction experts (N=5); User testing: PLWHA (N=20)	Quantitative and qualitative summary of heuristic violations; thematic analysis of think-aloud protocol, quantitative summary of mouse clicks, time, etc.

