- 6) Report at least 8 symptoms. Possible symptoms include: fatigue or loss of energy, sadness/depression, muscle aches/pains, difficulty falling asleep, difficulty staying asleep, nervousness/anxiety, difficulty remembering, pain/numbness/tingling in hands or feet, trouble concentrating, decreased sex drive, diarrhea/loose bowel movement, difficulty achieving or maintaining an erection (males only), shortness of breath, constipation/bloating/gas, thirst/dry mouth, difficulty with balance/clumsiness/dropping things frequently, unplanned weight changes, dizziness/lightheadedness, heartburn/acid reflux, dry eyes, changes in appetite, ringing in ears or intolerance to noise, cough, nausea/vomiting, fevers/chills, sweats, difficulty with urination, speech difficulties, pain or discomfort during sex
- 7) Taking antiretroviral therapy (ART).

While we anticipate that HANA conditions will be more prevalent in persons over age 50, we have not limited our inclusion criteria to this age range. We are collecting participants' age and will include that as a covariate in our final analysis. If our results in Aim 1 demonstrate a gross difference in symptom reporting and self-care strategies related to age of participants then the study team and external advisory board will meet and consider revising the inclusion criterion of age for the RCT.

Exclusion criteria include: pregnancy, unable to understand the consent procedure, and self-reporting no symptoms within the previous week or concurrent participation in a mobile app study for PLWHA including text messaging studies and any clinical problems that would not allow someone to use a cell phone or fulfill study procedures including meeting the criteria for dementia. Prior to participating in any study procedure, all potential participants must voluntarily provide informed consent.

Sample: We will recruit 5 PLWHA with HANA conditions to participate in a pilot and 100 PLWHA with HANA conditions to participate in a 6-month trial (see recruitment plan). They will be told the purpose of the study is to improve the quality of life of PLWHA. Sample size and statistical power calculations are based on the hypothesis test of improvement of symptom status after the use of VIP-HANA and on the comparison of the effect of VIP-HANA to the control group.

The intervention group will have access to VIP-HANA, a web app that provides self-care strategies tailored to symptom reporting, HANA condition(s) and gender. Both the control and

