intervention groups will receive reminders to complete their symptom assessments every week. Details of the difference between the study arms can be found in Table 2.

Table 2. Detailed Comparison of Intervention vs. Control Group		
	Intervention	Control
VIP-HANA: Self-care strategies tailored to symptom reporting, HANA condition(s) and gender	✓	
Symptom assessment every week	✓	✓
Secure messaging reminders to complete symptom assessment	✓	✓

The criterion for significance (alpha) has been set at 0.05 for the two-sided test. We will recruit 100 PLWHA with at least 1 HANA condition for the trial with a proposed sample size of 50 in each of the two groups. To account for a potential attrition rate of 20% by the end of study (week 26 or month 6 after the intervention), we propose to achieve a final sample of 80 patients (40 per group). Additionally, each patient will have a 20% chance to miss at least one of the symptom reporting points between week 2 and week 24 after the start of the intervention. We believe the 20% attrition assumption is conservative since our feasibility study had a 20% attrition rate we did not provide study participants with smartphones and data plans ([name], Wantland, Velez, Cato, & Jia, 2014).

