The power calculation for this study is not based on the feasibility study effect size as this was a pre-post study design and does not present equivalency to this study design. The purpose of the feasibility study was to show that participants are willing to use the system and that there was some meaningful change in symptom reporting after use of the VIP system (Bowen et al., 2009). The power analysis for this study is calculated to detect a clinically meaningful change in symptom frequency. For symptom frequency outcomes, 100 subjects gives more than 80.7% power to detect 13% decrease in symptom frequency (for example, from an average 8 symptoms to an average 7 symptoms) from the baseline to the end of study (i.e., 26th week). For the comparison between the control group and the VIP-HANA group, 100 subjects gives 82.4% power to yield a statistically significant result (assuming an intention-to-treat principle for the analysis) to test 10% difference in VIP-HANA over the control group (i.e., a decrease in symptom frequency). For the symptom intensity outcomes, the proposed sample yields at least 92.3% power to detect decrease in symptom intensity score of a small effect size of 0.1 from the baseline to the end of study. For the comparison of the two groups, this study will have about 87.4% power to yield a statistically significant result to test a small effect size of 0.24 difference in symptom intensity score for the VIP-HANA group over the control group.

Procedures

Recruitment Plan: We will post flyers at local clinics and community based organizations throughout New York City. Potential participants will be pre-screened for eligibility over the phone by study staff. In order to ensure that an eligible participant arrives at their visit, they will receive a confirmation email for their baseline visit which will be generated by REDCap.

Pilot: We will conduct a recruitment pilot that enrolls 5 PLWHA with at least 1 HANA condition

before the 6-month trial. This pilot will allow us to determine ease and feasibility of recruiting PLHWA that have HANA conditions, as well as examining any issues there may be in retention and adherence with regard to usage of the VIP-HANA app. Those enrolled in the pilot will follow the same procedure (randomization, data collection) as those enrolled in the 6-month trial.

Trial: We will enroll 100 PLHWA with HANA conditions in a 6 month trial with a baseline, 3 month and 6 month measurement.

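### Two primary outcomes are each tested at an unsplit two-sided 0.05, and no rule says whether one or both must be significant

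*Combined protocol and SAP*

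**What the plan says.** **Two primary outcomes.** Study Purpose and Rationale, and again the primary-outcome paragraph under Outcome Measures, state: "We hypothesize that VIP-HANA will improve symptom frequency and intensity, our primary outcomes". Hypothesis (a) of Specific Aim 2 reads: "Decrease symptom frequency and intensity (primary outcome measures) in the treatment arm as compared to the control arm".

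**Also described as one construct.** The Sample paragraph of Specific Aim 2 says: "Sample size and statistical power calculations are based on the hypothesis test of improvement of symptom status after the use of VIP-HANA", and adds the comparison with control as a second basis. Table 3 has a single primary entry, symptom status, measured by one checklist. The text after the table also speaks of one primary outcome.

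**One significance level.** After Table 2: "The criterion for significance (alpha) has been set at 0.05 for the two-sided test".

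**Separate powers.** The power paragraph opens with "The power analysis for this study is calculated to detect a clinically meaningful change in symptom frequency" and then gives four figures:
- frequency, baseline to end of study: "100 subjects gives more than 80.7% power to detect 13% decrease in symptom frequency"
- frequency, between arms, 10% difference: "100 subjects gives 82.4% power to yield a statistically significant result"
- intensity, baseline to end of study: "at least 92.3% power to detect decrease in symptom intensity score"
- intensity, between arms, effect size 0.24: about 87.4%

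**Separate models.** Data Management and Analysis assigns a linear mixed model to intensity and a negative binomial mixed model to frequency. It names no contrast (overall arm effect, arm-by-time, or week 26) and does not combine the outcomes.

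No section states a success rule, a testing order, an alpha split or a joint power.

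**The concern.** With two primary tests, the trial's error rate and its chance of success both depend on the decision rule, and the rule is absent. If both tests must succeed, error is controlled, but neither stated power is the chance that the trial succeeds. If one success is enough, the error of the primary conclusion can exceed 5%. If exactly one test is significant, the plan does not say whether efficacy has been shown, and the answer could be settled after the results are known.

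The symptom-status label does not close the gap. No combined score or joint test is defined, and the analysis section models two outcomes.

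**Working it through.** **Inputs.** Two-sided alpha 0.05 (Specific Aim 2, after Table 2). Between-arm powers 82.4% for frequency and 87.4% for intensity (power paragraph). The correlation ρ between the two test statistics is not given. It is assumed here over 0 to 1, and is probably positive because both outcomes come from the same weekly checklist.

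**1. Can the stated powers be reproduced?** Not from the documents.
- Intensity at a single time point, SD 1, 50 per arm: Φ(0.24 × √(50/2) − 1.96) = Φ(−0.76) = 22.4%. At 40 per arm it is 18.8%.
- Frequency, 10% below a mean of 8, Poisson, 50 per arm: SE of the log ratio = √[(1/8 + 1/7.2)/50] = 0.0726, so power = Φ(0.1054/0.0726 − 1.96) = about 31%. Overdispersion lowers it.
- Intensity averaged over 26 weekly reports reaches 87.4% only with a within-person correlation near 0.12 (50 per arm) or 0.08 (40 per arm).

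Repeated measures may be what the sponsor used, but the dispersion, within-person correlation and number of reports are not stated. The powers are therefore taken at face value below.

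**2. Noncentralities.** 1.960 + z(0.824) = 2.891 for frequency; 1.960 + z(0.874) = 3.105 for intensity.

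**3. Either suffices.** Family-wise error = 1 − P(|Z₁| < 1.96, |Z₂| < 1.96), with both means zero. At ρ = 0 this is 1 − 0.95² = 9.75%. It does not depend on the stated powers.

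**4. Both required.** Joint power = P(Z₁ > 1.96, Z₂ > 1.96), with means 2.891 and 3.105. At ρ = 0 this is 0.824 × 0.874 = 72.0%; at ρ = 1 it is the smaller power, 82.4%. Error is at most 5%, because a false joint claim needs at least one true null to be rejected at 0.05.

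**5. Exactly one significant.** Frequency only = 82.4% − joint power; intensity only = 87.4% − joint power.

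| Assumed ρ | Either suffices: family-wise error | Both required: joint power | Frequency only | Intensity only | Exactly one |
|---|---|---|---|---|---|
| 0 | 9.75% | 72.0% | 10.4% | 15.4% | 25.8% |
| 0.5 | 9.1% | 75.5% | 6.9% | 11.9% | 18.9% |
| 0.9 | 7.0% | 80.3% | 2.1% | 7.1% | 9.2% |
| 1 | 5% | 82.4% | 0% | 5.0% | 5.0% |

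Totals are taken from unrounded values. The last four columns assume jointly normal statistics and the stated effects.

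**6. Fixed sequence, frequency then intensity.** If there is no frequency effect, any false claim first needs frequency rejected at 0.05. If there is a frequency effect but none on intensity, a false claim needs intensity rejected at 0.05. Error is at most 5% either way. Power for frequency stays at the stated 82.4%; power for a confirmatory intensity claim becomes the joint power in the table.

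**7. Bonferroni, for comparison.** At 0.025 each the critical value is 2.241. Power is Φ(2.891 − 2.241) = 74.2% for frequency and Φ(3.105 − 2.241) = 80.6% for intensity.

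**The case against.** The strongest reply is that the documents already imply a both-required rule. One hypothesis joins the two outcomes with *and*, error is then at most 5%, and a single significant result leaves the hypothesis only partly supported. This carries weight: it is the more natural reading, and no section says either outcome suffices. But a hypothesis sentence is not a decision rule. Even on this reading, the power paragraph lacks the figure that matters, the chance that both tests succeed.

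A second reply is that outcomes from one checklist are probably well correlated, so the zero-correlation figures are the least plausible. That is fair, which is why the values at 0.5 and 0.9 are put first. At 0.9 the effect is smaller but not nil.

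A third reply is that putting frequency first is a reviewer's preference, since the documents present the outcomes as equals. The power paragraph says its calculation targets frequency, but it then powers intensity too. The order is therefore the sponsor's to choose, and a fixed sequence is one option among several.

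A reader might also infer that four primary tests are in play, because baseline-to-end powers are given alongside the between-arm ones. The documents do not support this: Aim 2 is a comparison with control, hypothesis (a) is between-arm, and the baseline-to-end figures appear only in the sizing text.

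**Conclusion.** The point holds as a missing decision rule that should be fixed. The omission itself is plain from the text; its size depends on a correlation that the documents do not give.

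The family-wise error range rests only on the assumed correlation and normal statistics. The joint-power range also rests on the two stated powers, which could not be reproduced; if they are too high, joint power is lower as well.

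Two stronger readings go too far. A reader might infer that the plan accepts a 9.75% error rate. It does not say so: that figure needs both a rule the documents never adopt and zero correlation. A reader might also take 72.0% to 82.4% as the trial's actual chance of success. It is only what the stated powers imply if both outcomes are required.

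**What to change.** Before outcome data are seen, amend the analysis and power paragraphs as follows.

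1. Name one between-arm contrast for each outcome. Without this, no rule refers to a defined test.
2. Adopt a rule that holds family-wise error at 5%. Two options fit the text:
   - *Fixed sequence.* Test frequency first at two-sided 0.05, then intensity at 0.05 only if frequency is significant. Efficacy is claimed on frequency if frequency is significant; an intensity claim needs both; an intensity-only result is exploratory.
   - *Both required.* If that is the intent, say so, and report joint power with the assumed correlation as the chance of success.
3. State that the baseline-to-end tests are not confirmatory.

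**Cost.** A short amendment, with no change to sample size or data collection. Under the fixed sequence, the chance of a confirmatory intensity claim falls from the stated 87.4% to the joint power (75.5% at correlation 0.5, 80.3% at 0.9), and an intensity-only result (11.9% and 7.1% respectively, under the stated effects) supports no efficacy claim. If both are required, that joint power becomes the whole trial's chance of success.

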Randomization: This will be a single-blinded study, with subjects blinded to study group assignment. Patients will be randomized (1:1) to VIP-HANA or an attention control group. Both groups will receive secure messaging reminders via their smartphone and will also be asked to report their symptoms on their smartphone via a web app every week. Participants in the VIP-HANA (intervention) group will also receive symptom strategies tailored to symptom reporting, HANA condition(s) and gender. Details of the differences between the intervention and control group can be found above in Table 5 (see Section D.1.b).

Data collection: We will have two levels of data collection.

- 1) Participants will report on their symptom frequency and intensity every week on the VIP-HANA app. Participants in both groups will receive reminder messages to report symptoms every week via the revised Sign and Symptom Check-List for HIV delivered via email. If a participant has not completed the checklist in more than 3 weeks, he/she will receive a reminder email or phone call. Intervention arm participants will complete the revised Sign and Symptom Check-List for HIV every week and receive tailored self-care strategies based on their symptom reporting, HANA condition, and gender. Control arm participants will complete the revised Sign and Symptom Check-List for HIV, but will NOT receive strategies.

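### The before-after power for symptom frequency (80.7%) is stated on 100 subjects although only 50 use VIP-HANA, and the 92.3% for intensity cannot be verified from its stated inputs

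*Combined protocol and SAP*

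**What the plan says.** All references are to the combined protocol and SAP, Specific aim 2.

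- **Hypothesis.** The Sample paragraph bases power on two tests. One is a "hypothesis test of improvement of symptom status after the use of VIP-HANA"; the other is the comparison with control.
- **Who uses VIP-HANA.** The trial recruits 100 people "with a proposed sample size of 50 in each of the two groups", with 40 per group expected to remain after 20% attrition. Under Randomization, "Patients will be randomized (1:1) to VIP-HANA or an attention control group". Table 2 gives the tailored strategies to the intervention column only, and item 1 of Data collection says that controls complete the checklist "but will NOT receive strategies".
- **Alpha.** "The criterion for significance (alpha) has been set at 0.05 for the two-sided test".
- **Before-after power, frequency.** "100 subjects gives more than 80.7% power to detect 13% decrease in symptom frequency", illustrated as "for example, from an average 8 symptoms to an average 7 symptoms", from baseline to week 26.
- **Before-after power, intensity.** "the proposed sample yields at least 92.3% power to detect decrease in symptom intensity score of a small effect size of 0.1", from baseline to the end of study.
- **Between-arm power.** 82.4% for frequency, again on 100 subjects, and 87.4% for intensity.

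No standard deviation, overdispersion, within-person correlation or number of visits is given for either before-after figure, and the unit of the 0.1 is not defined.

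**The concern.** A test of change after using VIP-HANA can draw only on people who used it, which is one arm of 50. The frequency power is nevertheless attached to 100 subjects, and in the next sentence the same phrase plainly means both arms together. Read as printed, the group for the stated hypothesis is counted at twice its size.

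The intensity figure raises a second question. An effect of 0.1 is very small for a sample of this size, and 92.3% is a high power for it without some further input.

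The before-after test is one of two stated bases for the sample size, and it covers both primary outcomes. A reader would take the VIP-HANA arm to have 81% to 92% power to show improvement, and could then read a non-significant change in that arm as evidence of no improvement.

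**Working it through.** **Inputs from the plan:** two-sided alpha 0.05 (z = 1.960); 50 per arm, 40 completers; a 13% fall, or 8 to 7 symptoms, with stated power 80.7%; effect size 0.1 with stated power 92.3%; baseline plus 26 weekly reports (27 points, Outcome Measures).

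**1. Can 80.7% be reproduced?** Not from the stated inputs alone, because no variance is given. As an assumption, take Poisson counts at two time points with within-person correlation ρ:

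power = Φ{(m1 − m2)/√[(m1 + m2 − 2ρ√(m1·m2))/n] − 1.960}

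| Fall | n | Power at ρ = 0 | ρ needed for 80.7% |
|---|---|---|---|
| 8 to 7 | 100 | 73% | 0.17 |
| 8 to 6.96 (13%) | 100 | 77% | 0.10 |
| 8 to 7 | 50 | 45% | 0.58 |
| 8 to 6.96 (13%) | 50 | 48% | 0.55 |

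Under this two-point model the printed figure is reached with 100 at a weak correlation, and with 50 only at a moderate one. That is compatible with 100 having been used but does not prove it.

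**2. Rescale to the VIP-HANA arm, if 100 was used.** This step needs no assumed SD.

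- Noncentrality behind 80.7%: 1.960 + 0.867 = 2.827.
- Half the sample: 2.827/√2 = 1.999; power = Φ(1.999 − 1.960) = Φ(0.039) = 51.6%.
- Going from 80 completers to 40 has the same ratio, so the result is the same.

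**3. Pool both arms, if controls do not change.** The mean change halves and n stays at 100: 2.827/2 = 1.413; power = Φ(1.413 − 1.960) = 29.2%, holding the SD of change fixed.

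**4. Intensity at face value.** A paired t-test with a standardized change of 0.1, two-sided 0.05 (noncentral t):

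| n | 100 | 80 | 50 | 40 |
|---|---|---|---|---|
| Power | 16.8% | 14.3% | 10.7% | 9.5% |

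One-sided with n = 100 gives 25.7%. Reaching 92.3% would need about (3.386/0.1)² ≈ 1,146 people, where 3.386 = 1.960 + 1.426.

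**5. What would make 92.3% attainable?** Each of these readings uses an input that the plan does not state:

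- 0.1 in raw-score SD units, two time points: 2(1 − ρ) = n(0.1/3.386)², so ρ = 0.956 with 100 or 0.978 with 50.
- Linear trend over 27 weekly points, random intercept only (Sxx = 1638; variance of the 26-week change = 676/1638 × (1 − ρ)/n): ρ = 0.79 with 100 or 0.89 with 50.
- Repeated-measures ANOVA over 27 visits with Cohen f = 0.1: 92.2% with n = 80 and ρ = 0.3; 92.5% with n = 50 and ρ = 0.57.

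**The case against.** The strongest reply is that the planned analysis is not a two-point paired test. Data Management and Analysis specifies mixed models on repeated symptom reports, and up to 27 reports per person carry far more information than two. With a linear trend, a random intercept and a one-symptom fall over 26 weeks, power = Φ{1/√[(676/1638)·v/n] − 1.960}, where v is the within-person variance. With n = 50 this is 97% at v = 8 (Poisson, mean 8) and 81% at v = 15. With n = 40 it is 94% at v = 8 and 81% at v = 12. Random slopes would lower all of these. The intervention arm alone could therefore meet 80.7%, and 100 subjects may be no more than a label for the trial. This stands: the 52% is conditional on 100 having entered the calculation, and the documents do not settle that.

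A reader might also infer that both before-after powers are stated on 100. The text does not say so. The intensity figure refers to the proposed sample, and the same section uses a similar phrase for 50 per group. Rescaling 92.3% to about 67% would lean on that inference and would treat an unverified figure as a sound base. Nor do the documents show that 92.3% is unattainable, since ordinary correlations in a repeated-measures formula reach it.

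Finally, the Aim 2 hypothesis on symptoms is a comparison between arms, and the analysis section prespecifies no within-arm before-after test. This limits the practical harm. It does not remove the mismatch, because the Sample paragraph names the before-after test as a basis for the sample size. Pooling the arms would explain the 100 but would not test that hypothesis.

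**Conclusion.** The concern holds in a limited form. The 80.7% is stated on twice the number of people to whom its hypothesis applies. If 100 was used, power in the VIP-HANA arm is about 52% with the same variance inputs, for 50 of 100 enrolled or 40 of 80 completers. If the arms are pooled and controls stay unchanged, it is about 29%. If 50 was already used, 80.7% may stand, but only under variance and correlation inputs that the plan omits.

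The 92.3% does not follow from effect size 0.1 and two-sided 0.05, which give about 17% with 100 and 11% with 50 in a plain paired test. It may follow from other inputs, so it cannot be verified as written.

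A reader might conclude that the trial is underpowered for its main comparison. This point does not support that: the between-arm powers of 82.4% and 87.4% are separate calculations and are not affected. The correction is worth making because it is cheap and the figures describe both primary outcomes.

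**What to change.** In the power paragraph of Specific aim 2:

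- Recompute and restate both before-after powers for the VIP-HANA arm (50 enrolled, 40 completers) under the planned mixed models. State the SD or dispersion, the within-person correlation, the number of visits used and what the 0.1 measures.
- If 100 was used with the existing inputs, replace 80.7% with about 52%.
- If the test pools both arms, stop describing it as improvement after VIP-HANA use.
- Withdraw the 92.3% if no stated input supports it. Do not substitute 67%, which only rescales the unverified figure.

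The cost is one recalculation and a rewritten paragraph, with no added participants or procedures. The stated powers may become less favourable.
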